### Statistical Analyses [\*]

The required sample size was determined by power analysis based on previous studies. [G \* Power, Version: 3.1.9.2 Statistical Packages, Power Analysis for Repeated (ANOVA) Type 1 error probability was 0.05%, power of the test was 80%.] The minimum required number of people for each group was calculated as 17. It was predicted that 10% of the patients would be excluded during the study, and a total of 38 patients were planned to be included in the study, including 19 in each group.

Descriptive statistics of numerical variables will be given as mean, standard deviation, median, minimum and maximum. Descriptive statistics of qualitative variables will be given as numbers and percentages. Whether numerical variables show normal distribution will be investigated with Shapiro Wilk test.

In the comparison of two independent groups, Student's t test will be used for variables with normal distribution and Mann Whitney U test will be used for non-normally distributed variables. In comparing two dependent groups, Paired t test will be used for variables with normal distribution and Wilcoxon test will be used for non-normally distributed variables. A statistical significance level of 0.05 will be taken,  $p < 0.05$  will be considered statistically significant. SPSS package program will be used in calculations.

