### Baseline Measure Information \*

Patients' age, gender, educational status, height and weight, additional diseases, medications used, time after the patient's stroke, duration of hospitalization in the acute period after stroke, stroke type (ischemic / hemorrhagic), lesion region, degree of ambulation according to functional ambulation classification will be recorded at the beginning of the study. The change in Functional Oral Intake Scale (FOIS) will be our primary outcome measure in our research.

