### ▼3. Outcome Measures

#### Primary Outcome Measure:

- Change in Functional Oral Intake Scale (FOIS)

Functional Oral Intake Scale (FOIS) is a scale that shows the functional oral intake of patients with dysphagia. FOIS used for evaluation is a two part scale consisting of 7 levels. It is used to show whether the individual is dependent on the feeding tube and the level of oral intake. On this scale, 7 shows the best and 1 shows the worst functional oral intake. The change in FOIS will be our primary outcome measure in our research. It has been evaluated as an appropriate tool to demonstrate the change in functional oral intake in stroke patients. It is suitable as an independent measure of functional oral intake in prospective studies of stroke-related dysphagia.

[Time Frame: before intervention, immediately after intervention, 3 months after the intervention]

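### Cheap improvement: FOIS is scheduled before treatment, but the planned between-arm test does not adjust for it; the test is valid but usually less efficient than a baseline-adjusted one.

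*Combined protocol and SAP*

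**What the plan says.** The Primary Outcome Measure section states: "The change in FOIS will be our primary outcome measure in our research". Its schedule reads "Time Frame: before intervention, immediately after intervention, 3 months after the intervention", so a pre-treatment value is planned for every patient. The same section describes the scale: "FOIS used for evaluation is a two part scale consisting of 7 levels".

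The Statistical Analyses section checks normality with Shapiro-Wilk. For the comparison between arms, its rule is this: "Student's t test will be used for variables with normal distribution and Mann Whitney U test will be used for non-normally distributed variables". Paired t and Wilcoxon tests are listed for within-group comparisons. No ANCOVA, mixed model or other baseline-adjusted method is named. The section does not say which of the two follow-up visits carries the comparison between arms.

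On size, "The minimum required number of people for each group was calculated as 17", raised to 19 per group for 10% exclusions. The method given is "Power Analysis for Repeated (ANOVA"), which does not reappear among the planned analyses. On significance, "A statistical significance level of 0.05 will be taken".

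**The concern.** Since the outcome is change in FOIS, the natural reading is that baseline enters only by subtraction. Subtraction fixes the weight on baseline at one. ANCOVA estimates that weight from the data, so the change score matches it only when the baseline/follow-up correlation r is close to the ratio of baseline SD to follow-up SD. Elsewhere the change score carries avoidable noise.

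The trial plans on 17 evaluable patients per arm, so precision matters, and the covariate is already being collected. What is at stake is power, not bias.

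**Working it through.** **The plan's own figure.** 17 / 0.90 = 18.9, rounded up to 19 per group and 38 in total, so the dropout step reproduces. The 17 itself cannot be derived, because no effect size, SD or correlation is given. It can be matched with assumed inputs: a within-between repeated-measures ANOVA with f = 0.25, correlation 0.5 and two measurements gives N = 34. The type 1 error is printed as 0.05%. It is read here as 0.05, because a literal 0.0005 with the same inputs gives N = 82.

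**Inputs.** From the plan: 17 per arm and significance level 0.05 (two-sided assumed). Assumed: r, k = baseline SD / follow-up SD, and an anchor of 80% power for the change-score t test. The plan's 80% belongs to a repeated-measures ANOVA, so the anchor is a convenience.

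**Formulae**, with follow-up SD set to 1:
- Variance of change: 1 + k² − 2rk.
- ANCOVA residual variance: 1 − r².
- Ratio V = (1 − r²) / (1 + k² − 2rk). This equals 1 when k = r, and (1 + r)/2 when k = 1.
- The t test (32 df) has 80% power at 0.991 SD of change, a noncentrality of 0.991 × √(17/2) = 2.889.
- ANCOVA (31 df) has noncentrality 2.889 / √V. To charge for estimating the slope, V is multiplied by 1 + 1/(2 × 17 − 4) = 1.033.

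**Worked cases.**
- k = r: V = 1. Power is 78.6% after the slope charge, 1.4 points below the t test.
- r = 0.5, k = 1: V = 0.75. Power is 89.8% (88.9% after the charge).
- r = 0.3, k = 1.2: V = 0.91 / 1.72 = 0.529. Power is 97.0% (96.6% after the charge).

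**Grid.** ANCOVA power in %, before / after the slope charge:

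| k | r = 0.3 | r = 0.5 | r = 0.7 | r = 0.8 | r = 0.9 |
|---|---|---|---|---|---|
| 0.7 | 85.9 / 84.7 | 81.9 / 80.7 | 79.9 / 78.6 | 81.0 / 79.7 | 86.8 / 85.8 |
| 0.8 | 88.5 / 87.5 | 84.2 / 83.0 | 80.7 / 79.4 | 79.9 / 78.6 | 81.9 / 80.6 |
| 1.0 | 93.5 / 92.7 | 89.8 / 88.9 | 85.9 / 84.8 | 83.9 / 82.7 | 81.9 / 80.6 |
| 1.2 | 97.0 / 96.6 | 94.9 / 94.3 | 92.7 / 91.9 | 92.0 / 91.1 | 92.5 / 91.7 |

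With equal SDs, the change-score t test would need 25/22/20/19/18 patients per arm to match the slope-charged ANCOVA at 17. If nobody drops out (19 per arm), the t test starts at 84.4%, and the equal-SD gains before the slope charge are 11.3, 8.5 and 5.2 points at r = 0.3, 0.5 and 0.7.

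**Discrete, skewed change.** The formulae compare ANCOVA with a t test, but the plan sends non-normal variables to Mann-Whitney. Illustrative simulations at 17 per arm, all inputs assumed:
- Strong skew, baseline over levels 1–5. Gains of 0/1/2/3/4 levels: control 60/20/5/5/10%, NMES 15/55/15/5/10%. Mann-Whitney was chosen in over 99% of trials. Power: planned rule 55%, linear ANCOVA about 33%, rank analysis of change adjusted for ranked baseline about 55%.
- Milder skew, baseline over levels 1–6: control 50/30/10/5/5%, NMES 15/40/30/10/5%. Power: planned rule 55%, linear ANCOVA 45%, adjusted rank analysis of change about 54%.

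Linear ANCOVA therefore loses 55 − 33 = 22 and 55 − 45 = 10 points. Ranking the follow-up score instead of the change does not help (32% and 42%).

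**Rounded normal scores clipped to 1–7.** The adjusted rank analysis of change had about 65% power against 52% for the planned rule at k = 1, r = 0.3, and no gain at k = 0.7, r = 0.7.

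**The case against.** The strongest objection is that a loss of about one point is no ceiling on the cost of linear ANCOVA. FOIS change is a small integer, Shapiro-Wilk will often reject, and the plan then uses Mann-Whitney, which can be much the better test. This stands. A reader might infer from the grid that linear ANCOVA should simply become the sole primary analysis at negligible risk. The documents do not support that, because they say nothing about the shape of FOIS change. The objection applies to that remedy and not to baseline adjustment itself, since the adjusted rank analysis of change kept pace with the planned rule in both skewed settings.

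It is also fair that r, the SDs and the effect size are absent, so the range reflects the values chosen. More extreme inputs go slightly above 97%, so that is not an upper limit.

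A third objection is that nothing in the plan is wrong. That is correct as to validity. A reader might infer bias or an inflated type 1 error from the missing covariate, but randomisation makes the unadjusted comparison valid.

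Finally, the repeated-measures ANOVA in the sample-size sentence might be taken as the intended analysis. It is not listed among the analyses, and the text should not be read as though it were.

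**Conclusion.** The point holds as an efficiency improvement that the sponsor should make. Baseline FOIS is scheduled and the between-arm test does not adjust for it. Against a change-score t test anchored at 80% power, linear ANCOVA ranges from a loss of 1.4 points to a gain of about 17 points over the values shown, with about 10 points at r = 0.5 and equal SDs. This rests on an assumed anchor, assumed r and SDs, and normal linear theory.

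Against the Mann-Whitney route the sign of the difference for linear ANCOVA depends on the shape of the data. A rank analysis of change adjusted for ranked baseline ranged from roughly level to a gain of about 13 points (65 − 52) in the illustrative settings. The true gain in this trial cannot be determined from the documents.

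**What to change.** In Statistical Analyses, keep the parametric/non-parametric structure but adjust both branches for baseline FOIS, at one follow-up visit named before the data are seen:
- in place of the t test, a linear ANCOVA of FOIS at that visit on arm and baseline FOIS;
- in place of Mann-Whitney, a rank analysis of change in FOIS, adjusted for ranked baseline FOIS.

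Alternatively, because FOIS has only 7 levels, make the rank analysis the single primary test. In either case, report the other model as the sensitivity analysis.

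The cost is one residual degree of freedom, about one point of power where the change score is already near-optimal, a few sentences of text and slightly more analysis work. No extra patients, visits or measurements are needed. The same adjustment may be used for EAT-10, SWAL-QOL, VAS and V-RQOL, but no gain has been calculated for them.

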## ▼4. Adverse Event Information

Information for completing three tables summarizing adverse events.

1. All-Cause Mortality: \* § Mortality is not expected in our study.
2. Serious Adverse Events: \* Serious adverse events are not expected in our study.
3. Other (Not Including Serious) Adverse Events: \* Adverse event due to the study is not expected. If any adverse event will be seen it will be reported.

### Time Frame \* §

Adverse event data will be collected between 15 April 2020 and 15 April 2021.

### Adverse Event Reporting Description [\*]

Patients will be invited for a checkup immediately after the intervention and three months

after the intervention. When patients encounter any problem beyond the specified times, they will reach out to the researcher through the contact number given to them and report the problem.

**Collection Approach for Table Default** \* § (or *Collection Approach for each Adverse Event Term required*)

Systematic Assessment: Patients will be invited for a checkup immediately after the intervention and three months after the intervention.

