**Organ System \***

General Disorders

**Collection Approach \*** § (or Collection Approach for Table Default required)

Systematic Assessment: Patients will be invited for a checkup immediately after the intervention and three months after the intervention.

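### For a patient who misses the 3-month checkup, the only described adverse event route is the patient's own call, so deaths and serious events in non-attenders can go unrecorded

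*Combined protocol and SAP*

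**What the plan says.** All references are to the combined protocol and SAP.

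- **Checkups.** Section 4, under Organ System / Collection Approach, and in the same terms under Adverse Event Reporting Description: "Systematic Assessment: Patients will be invited for a checkup immediately after the intervention and three months after the intervention".
- **All other times.** For problems outside those checkups, Adverse Event Reporting Description says of patients that "they will reach out to the researcher through the contact number given to them and report the problem".
- **Expectation.** The opening of section 4 states "Mortality is not expected in our study" and "Serious adverse events are not expected in our study". The item on other, non-serious events adds "If any adverse event will be seen it will be reported".
- **Table entries.** The rows for deaths, serious events and other events show 0 affected and also 0 at risk, although 38 patients are planned.
- **Attrition.** Section 3, Statistical Analyses: "It was predicted that 10% of the patients would be excluded during the study". The text does not say when or why patients would be excluded, or whether contact with them continues.

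The documents describe no scheduled call between the checkups, no contact with a relative or carer, no check of records and no action after a missed checkup.

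**The concern.** These are post-stroke patients with dysphagia. Section 3 grades penetration and aspiration and looks for vocal cord paresis, so the plan itself treats airway and voice problems as relevant to this population. In the three months after therapy, the safety record depends on a patient either accepting an invitation or contacting the researcher. A patient who has died can do neither, and one who is seriously ill in hospital may be able to do neither.

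The error runs in one direction. An event that nobody learns of leaves its row at zero, and the table then looks safer than the truth. With 19 patients per arm, a single missed death or admission is a visible share of that arm's record. A reader of the finished table could not tell whether a zero means that everyone was traced and well, or that some patients were never reached.

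**Working it through.** **1. The plan's own attrition figure.** Inputs from Statistical Analyses: 17 needed per group, 10% exclusions. 17 / (1 − 0.10) = 18.9, rounded up to 19 per group and 38 in total, which matches the plan. The allowance is 19 − 17 = 2 per arm, or 38 − 34 = 4 overall (10% of 38 = 3.8).

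**2. Which route reaches whom.**

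| Situation | Described route |
|---|---|
| During therapy (5 days × 3 weeks = 15 sessions) | Patient's own report; staff see the patient, but sessions are not named as collection points |
| Problem after therapy, patient attends at 3 months | Patient's own report, or the 3-month checkup, though the plan does not say that it asks about the interval |
| Problem after therapy, patient misses the 3-month checkup | Patient's own report only |
| Death before the 3-month checkup | None that can work: the patient can neither attend nor call |

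The last row does not depend on the 10%. Anyone who dies in the interval is by definition a non-attender.

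**3. Size of one missed event.** 1/19 = 5.3 percentage points in its arm.

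**4. How likely is a missed event?** The documents give no event rate, so I assume a per-patient risk p of death or admission, the same for all patients, and show a range. I also assume that the 4 excluded patients lose contact.

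| Assumed p | At least one event among 38: 1 − (1 − p)^38 | At least one among 4: 1 − (1 − p)^4 |
|---|---|---|
| 1% | 32% | 4% |
| 2% | 54% | 8% |
| 5% | 86% | 19% |
| 10% | 98% | 34% |

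**5. How likely is a false zero?** Let each event be captured independently with probability c. The chance of recording none when at least one occurred is (1 − pc)^38 − (1 − p)^38.

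| Assumed p | c = 50% | c = 90% |
|---|---|---|
| 2% | 0.683 − 0.464 = 22% | 0.501 − 0.464 = 4% |
| 5% | 0.382 − 0.142 = 24% | 0.174 − 0.142 = 3% |
| 10% | 0.142 − 0.018 = 12% | 0.028 − 0.018 = 1% |

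The 90% column is close to the case in which only the four non-attenders' events are missed (34/38 = 89%). The 50% column also needs events to be missed in attenders, which is possible only if the checkup does not ask about the interval.

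**6. What a true zero would be worth.** Even with every patient traced, 0/38 has a one-sided upper 95% limit of 1 − 0.05^(1/38) = 7.6%, and 0/19 in one arm has 1 − 0.05^(1/19) = 14.6%. A zero from incomplete tracing supports less than that.

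**The case against.** The strongest reply is that the gap is narrow. Several stronger readings are tempting, and the documents do not support them.

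- **That interval events are known only if the patient calls.** This fails for attenders. The 3-month checkup is a named collection point and can pick up earlier admissions or infections. What remains is that the plan does not say it asks about them.
- **That the plan forecasts losing contact with 10%.** It forecasts exclusion. Some exclusions could fall within the three weeks of near-daily therapy, when staff see the patient. The figure of 4 is therefore an assumption.
- **That 4/19 (21%) of an arm could be hidden behind a zero.** This needs all four exclusions in one arm, an event in each and none recorded. The sample size allowance is 2 per arm.
- **That the zeros are results, or that non-attenders will be counted as event-free.** Zero affected beside zero at risk looks like a placeholder. The plan undertakes to report events that are seen, and Period(s) in section 1 promises patient numbers at the start and end, so attrition would be visible. No text tells the analyst to treat silence as no event.
- **That the telephone route is mislabelled as systematic.** The words after that label describe only the two checkups.

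Two further cautions stand. The documents do not show that the sickest patients are the likeliest to miss a visit; only for death does that follow by logic. The contact and consent pages are not in the public text, so a carer contact may already be collected there.

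None of this supplies a step for the patient who does not attend. The undertaking to report events depends on someone seeing them.

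**Conclusion.** The point holds in its narrow form. For a patient who misses the 3-month checkup, self-report is the only route described, and in the worst cases it cannot work. For attenders, the plan leaves open whether events since the last contact are asked about. As written, a confirmed zero and an unknown would look alike in the adverse event tables.

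The firm size is 5.3 percentage points per missed event in an arm of 19. How often this would happen cannot be derived from the documents. With 4 non-attenders and a risk of 1% to 10% each, both assumed, the chance that at least one of them has an event is 4% to 34%.

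This is a worthwhile and inexpensive improvement to the safety data. It does not affect the FOIS comparison or the sample size.

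**What to change.** Amend Adverse Event Reporting Description in section 4 to say that:

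1. each checkup asks about and records deaths, hospital admissions and other adverse events since the last contact;
2. a carer or relative contact is recorded at baseline, with consent (if the consent pages already provide this, state that it will be used);
3. for anyone who misses a checkup or is excluded, the existing researcher phones the patient or carer to establish vital status and serious events through 3 months, and checks the study hospital's record where consent allows;
4. the adverse event tables give, per arm, the true number at risk and the number with unknown vital status. The present zeros should be left blank until there are counts to enter.

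The cost is a few phone calls (about four patients under the assumption above), one baseline form field and a line in the consent form, which must also cover the record check if that is used. Admissions to other hospitals would rest on the call. No new visit or procedure is needed.

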### **Arm/Group Information** \*

Patients who meet the inclusion criteria will be randomized into two groups by computer program after being enumerated according to the order of application. Traditional dysphagia therapy and neuromuscular electrical stimulation (NMES) will be applied to 19 patients selected for Experimental Group. Traditional dysphagia therapy will be applied to 19 patients selected for Active Comparator Group.

### **Arm/Group Title** \*

Arm: Experimental: Neuromuscular Electrical Stimulation (NMES) with TDT

Arm: Active Comparator: Traditional Dysphagia Therapy (TDT)

### **Arm/Group Description** \* §

Traditional dysphagia therapy and neuromuscular electrical stimulation (NMES) will be applied to 19 patients selected for the Experimental Group. NMES application and Traditional Dysphagia Therapy will be applied for 45 minutes a day, 5 days a week for 3 weeks.

Traditional dysphagia therapy will be applied to 19 patients selected for Active Comparator Group. Traditional Dysphagia Therapy will be applied for 45 minutes a day, 5 days a week for 3 weeks.

### **Total Number Affected by All-Cause Mortality** \* §

0

### **Total Number at Risk for All-Cause Mortality** \* §

0

### **Total Number Affected by Any Serious Adverse Event** \*

0

**Total Number at Risk for Serious Adverse Events \*** (or Number at Risk for each Serious Adverse Event Term required)

0

**Frequency Threshold for Reporting Other (Not Including Serious) Adverse Events \***

5

**Total Number Affected by Any Other (Not Including Serious) Adverse Event Above the Frequency Threshold \***

0

**Total Number at Risk for Other (Not Including Serious) Adverse Events \*** (or Number at Risk for each Other, [Not Including Serious], Adverse Event Term required)

0

**Adverse Event Term \***

Unexpected impact that affects the course of the study.

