# ClinicalTrials.gov Results Data Element Definitions for Interventional and Observational Studies

## ▼1. Participant Flow

Enrollment

Arms	Assigned Interventions

Experimental: Neuromuscular Electrical Stimulation (NMES) with TDT
	
Device: Procedure: Neuromuscular Electrical Stimulation with TDT
 
The skin to be treated will be cleaned and dried. NMES will be implemented with signals received from two channels. In the first channel, the upper electrodes will be placed horizontally just above the hyoid bone. This is the place where the cupping is felt when the finger is pressed right under the chin. In the second channel, the lower electrodes will be placed horizontally, just above the thyrohyoid muscle. This is the place where you can feel a cupping when pressed with your finger, on both sides of the apple in the larynx. The device will be set to start at the lowest power, with very short pulses of approximately 700 microseconds, at intervals of 1 second. The power will be gradually increased according to the device and the power that the patient feels vibration will be stopped. The power to be applied will not exceed 25 milliamps. NMES application and Traditional Dysphagia Therapy will be applied for 45 minutes a day, 5 days a week for 3 weeks.

Active Comparator: Traditional Dysphagia Therapy (TDT)
	
Behavioral: Procedure: Traditional Dysphagia Therapy (TDT)
 
Traditional dysphagia therapy includes diet modification training, teaching postural compensatory methods, training of oral motor control exercises and tongue root exercises, training of swallowing maneuvers, and practice of chin-resistance exercise, which is the exercise of opening the upper esophageal sphincter.
 
Traditional Dysphagia Therapy will be applied for 45 minutes a day, 5 days a week for 3 weeks.

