FEES will be performed by the otolaryngologist doctor before and immediately after the treatment. In the fiberoptic endoscopic swallowing assessment, the condition of the patient according to the penetration aspiration scale will be checked. Grade 1 represents the best and grade 7 the worst on the penetration aspiration scale.

[Time Frame: before intervention, immediately after intervention]

- Change in Voice-Related Quality of Life (V-RQOL) Score

This ten-item scale is a scale designed for adult populations with voice disorders to measure both social-emotional and physical-functional aspects of voice problems. The answer points for each question range from 1 (few problems) to 5 (serious problems). A total score change on this scale will be used to evaluate patients.

[Time Frame: before intervention, immediately after intervention, 3 months after the intervention]

Arms	Assigned Interventions

Experimental: Neuromuscular Electrical Stimulation (NMES) with TDT
	
Device: Procedure: Neuromuscular Electrical Stimulation with TDT
 
The skin to be treated will be cleaned and dried. NMES will be implemented with signals received from two channels. In the first channel, the upper electrodes will be placed horizontally just above the hyoid bone. This is the place where the cupping is felt when the finger is pressed right under the chin. In the second channel, the lower electrodes will be placed horizontally, just above the thyrohyoid muscle. This is the place where you can feel a cupping when pressed with your finger, on both sides of the apple in the larynx. The device will be set to start at the lowest power, with very short pulses of approximately 700 microseconds, at intervals of 1 second. The power will be gradually increased according to the device and the power that the patient feels vibration will be stopped. The power to be applied will not exceed 25 milliamps. NMES application and Traditional Dysphagia Therapy will be applied for 45 minutes a day, 5 days a week for 3 weeks.

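### The only adverse event term is narrower than the plan's own promise to report any adverse event, so minor events that do not disturb the study may go uncounted

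*Combined protocol and SAP*

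**What the plan says.** All of this is in section 4 (Adverse Event Information) of the combined protocol and SAP, unless another section is named.

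- **Adverse Event Term:** one entry, "Unexpected impact that affects the course of the study".
- **Organ System:** one entry, "General Disorders".
- **Opening of section 4:** deaths, serious events and other events are listed separately. On serious events it says "Serious adverse events are not expected in our study". On other events it says "Adverse event due to the study is not expected. If any adverse event will be seen it will be reported".
- **Adverse Event Reporting Description:** patients have two checkups, at the end of the intervention and three months after it. Between these they can contact the researcher about a problem of any kind.
- **Count fields** (deaths, serious events, other events, participants affected and participants at risk): all already filled with 0.
- **Section 1 (Participant Flow):** electrodes are used only in the experimental arm, and "The power to be applied will not exceed 25 milliamps".
- **Section 3 (Secondary Outcome Measures):** at the endoscopic swallowing evaluation, "the condition of the patient according to the penetration aspiration scale will be checked". This is done before and immediately after treatment, as an outcome measure.

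The document contains no other adverse event term, no general definition of an adverse event and no list of anticipated events.

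**The concern.** Read literally, the term sets two conditions: the event must be unexpected, and it must affect the course of the study. The opening of section 4 sets neither. Someone filling in the form with only this document could apply either rule, and two people could classify the same event differently.

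Both arms receive traditional dysphagia therapy, and the experimental arm adds NMES. The safety question particular to this trial is therefore whether stimulation adds local effects. Those are typically the events that can be handled without interrupting therapy, and so the ones most easily judged not to have affected the study. If they drop out of the table, they drop out mainly from one arm, and the comparison looks more favourable to NMES than the data warrant.

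**Working it through.** The plan gives no figure to reproduce here. The check is to set the entries side by side and then see how much the wording could matter.

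**Step 1: what each entry requires of an event.**

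| Entry in section 4 | Must be unexpected? | Must affect the study? |
|---|---|---|
| Opening statement on other events | No | No |
| Reporting Description (contact between visits) | No | No |
| Adverse Event Term | Yes, read literally | Yes, read literally |

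The first two concern reporting and collection. The third is the only category offered for recording what was reported. Nothing ranks them.

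**Step 2: which condition restricts.** The plan says "Adverse event due to the study is not expected" and "Serious adverse events are not expected in our study". With nothing expected, a rater can treat every event as unexpected, so the first condition need not exclude anything. The second does restrict: a mild electrode-site reaction that leaves therapy and follow-up intact does not meet it.

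**Step 3: could the reporting threshold be the restrictive element instead?** The Frequency Threshold entry is 5, with no unit. Assume it means 5% within an arm. One affected patient of 19 is 1/19 = 5.3%, which already exceeds it. On that reading the threshold would hide nothing at arm level.

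**Step 4: illustration with assumed rates.** Let p be the true proportion of NMES patients with an event and s the share of those events that meet the term. Neither is in the documents. With n = 19 independent patients, the chance of counting no event is (1 − p·s)^19.

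| Share s meeting the term | p = 10% | p = 20% |
|---|---|---|
| 100% | 0.90^19 = 13.5% | 0.80^19 = 1.4% |
| 50% | 0.95^19 = 37.7% | 0.90^19 = 13.5% |
| 25% | 0.975^19 = 61.8% | 0.95^19 = 37.7% |
| 0% | 100% | 100% |

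The expected number of patients with an event is 19 × 0.10 = 1.9 or 19 × 0.20 = 3.8. The table shows how sensitive an empty result is to s. It does not estimate any actual loss.

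**The case against.** The strongest reply is that the term is a placeholder. The document follows a results-reporting template, and the term sits beside count fields filled with 0. Zero participants at risk cannot describe a trial of 38 patients, so these fields look unfinished rather than operative. Nothing says that an event counts only if it fits the phrase, and the opening of section 4 commits to reporting any event seen.

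Much of this stands, and it rules out several stronger readings that a reader might infer:

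- *That foreseeable or non-disruptive events are definitely not counted.* The broad commitment and the open reporting channel point the other way. The conflict makes the outcome uncertain; it does not settle it as exclusion.
- *That an aspiration-related chest infection is excluded because it is foreseeable in these patients.* The documents list no anticipated events and say none is expected. Foreseeability would be the reader's inference.
- *That deaths and serious events are lost.* They have their own rows, and nothing shows that the term governs those rows.
- *That the single organ class bars other classes.* One row takes one class, and no text forbids further rows.

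What the reply does not remove is the gap. Placeholder or not, the phrase is the only event term in the document, and it contradicts the opening statement. The swallowing evaluation does not fill the gap either: it grades aspiration as an outcome at two time points, and records neither clinical events nor anything at three months.

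**Conclusion.** The point holds as an inconsistency. The single event term is narrower than the plan's own reporting commitment, and no definition decides between them. Non-serious events that do not disturb the study may go uncounted, with local reactions in the NMES arm the clearest example, and a report of no adverse events could partly reflect the wording.

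The size of the loss cannot be stated, because the documents give neither event rates nor the share of events that would fit the term. The illustrative range rests wholly on assumed values. The examples of electrode-site and aspiration-related events are inferred from the device and the population; the plan does not name them. The documents do not support saying that such events will be left out, only that they could be. This is a worthwhile, inexpensive correction that touches neither the treatment nor the primary analysis.

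**What to change.** Reconcile the Adverse Event Term entry with the opening of section 4. Suggested wording: *an adverse event is any untoward medical event from the first therapy session to the 3-month checkup, whether or not it was expected, is thought related to therapy, or affects the study.*

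Then:

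- Record each event under its own term and organ system, in place of the single general class.
- Tabulate events by arm, and note relatedness separately so that it does not decide whether an event is counted.
- At the two checkups already planned, ask both arms the same questions about local reactions at the electrode or neck area and about aspiration-related events.
- Keep the existing separate rows for deaths and serious events.

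The cost is a change of wording and a short event form; no visit is added. The downside is a longer table, with many events unrelated to therapy.
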